7.3. Method of Assignment to Treatment

7.3.1. Part A: Dose Escalation (Phase 1a)

A patient who meets all criteria for enrollment will be assigned (by the sponsor) to receive study treatment. Before each patient's enrollment into the study, an eligibility check must be conducted between the investigational site and the Lilly clinical research personnel to confirm that each patient meets all enrollment criteria. Upon confirmation of eligibility, the sponsor will confirm the dose and identification number assignment and cohort for each patient.

If investigators have eligible patients who have consented concurrently, more than 3 patients may be assigned to a particular dose level provided that accrual has not ceased due to excessive toxicity. This enrollment procedure is allowed because of the advanced disease state of this patient population and the screening involved in defining eligibility. Assigning more than 3 patients to a particular dose level should be approved by the sponsor following discussions with the investigators.

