7.2.2. Part A: Dose Escalation (Phase 1a)

By nature of being a dose-escalation study, data will be evaluated on an ongoing basis until the MTD is determined. Safety data, in particular AEs, will be the primary criteria for the dose escalation. No dose escalation can occur without prior discussion and agreement between the investigator, the Lilly study team, and the collaborator; the decision will be documented in writing.

Based on the ongoing safety reviews, modifications to the dose-escalation strategy or other design elements may be made via protocol amendment to ensure patient safety. No intrapatient dose escalation is permitted for any patient. Dose escalation may be ceased at any time based on available safety and PK behavior.

In Part A, study drugs for the LY3022855-plus-durvalumab and LY3022855-plus-tremelimumab combinations may be administered at the dose regimens shown in [Table JSCC.1](#) and

Table JSCC.2, respectively. Refer to Section 7.2.2.2 for further details on the planned dose-escalation method, proceeding from Cohorts D1a and T1a.

Table JSCC.1. Part A (Dose Escalation) Dose Regimens for the LY3022855-plus-Durvalumab Combination, by Cohort

Cohort	LY3022855		Durvalumab	
	Dose (mg)	Frequency	Dose (mg)	Frequency
D1a	25	QW	750	Q2W
	D1b ^a	25 Days 1, 8, and 15 of each cycle	750	Q2W
	D1c	25 Q2W	750	Q2W
D2a	50	QW	750	Q2W
	D2b ^a	50 Days 1, 8, and 15 of each cycle	750	Q2W
	D2c	50 Q2W	750	Q2W
D3a	75	QW	750	Q2W
	D3b ^a	75 Days 1, 8, and 15 of each cycle	750	Q2W
	D3c	75 Q2W	750	Q2W
D4a	100	QW	750	Q2W
	D4b ^a	100 Days 1, 8, and 15 of each cycle	750	Q2W
	D4c	100 Q2W	750	Q2W

Abbreviations: QW = weekly; Q2W = every 2 weeks.

Note: A cycle is defined as 28 days (4 weeks). QW refers to dosing on Days 1, 8, 15, and 22 of each cycle; Q2W refers to dosing on Days 1 and 15 of each cycle.

^a Enrollment to the Dnb cohort will occur only if ≥ 2 DLTs are observed after Cycle 1, Day 21 of the corresponding Dna cohort.

Table JSCC.2. Part A (Dose Escalation) Dose Regimens for the LY3022855-plus-Tremelimumab Combination, by Cohort

Cohort	LY3022855		Tremelimumab	
	Dose (mg)	Frequency	Dose (mg)	Frequency ^a
T1a	50	QW	75	Q4W
	T1b ^b	50 Days 1, 8, and 15 of each cycle	75	Q4W
	T1c	50 Q2W	75	Q4W
T2a	100	QW	75	Q4W
	T2b ^b	100 Days 1, 8, and 15 of each cycle	75	Q4W
	T2c	75 Q2W	75	Q4W
T3a	100	QW	225	Q4W
	T3b ^b	100 Days 1, 8, and 15 of each cycle	225	Q4W
	T3c	100 Q2W	225	Q4W
	T3d	75 QW	225	Q4W
T4a	100	QW	750	Q4W
	T4b	100 Q2W	750	Q4W

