- Grade 3 or 4 neutropenia that is not associated with fever or systemic infection that improves by at least 1 grade within 3 days. Grade 3 or 4 febrile neutropenia will be a DLT regardless of duration or reversibility
- Grade 3 or 4 lymphopenia
- Grade 3 thrombocytopenia that is not associated with clinically significant bleeding that requires medical intervention, and improves by at least 1 grade within 3 days
- Isolated Grade 3 electrolyte abnormalities that are not associated with clinical signs or symptoms and are reversed with appropriate maximal medical intervention within 3 days

- Isolated asymptomatic Grade 3 elevation of amylase or lipase without evidence of end organ damage.
- Asymptomatic Grade 3 CK level ($5-10 \times \text{ULN}$: CTCAE v4.0) that is not associated with elevated serum or urinary myoglobins and no evidence of rhabdomyolysis or myositis.
- Asymptomatic Grade 3 AST induction that is accompanied by Grade ≤ 1 ALT and Grade ≤ 1 TB and no change of ALT or TB from baseline levels.

Adverse events meeting DLT criteria that occur beyond Cycle 1 are defined as dose-limiting equivalent toxicities (DLETs). If a patient is believed to be benefitting from study treatment, patients who experience a DLT may continue to receive study treatment upon agreement of the investigator, sponsor, and collaborator.

For the purpose of this study, the MTD is defined as the highest tested dose that has less than 33% probability of causing a DLT. The MTD will be determined as shown in [Table JSCC.3](#) and [Table JSCC.4](#).

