7.2.2.2. Dose-Escalation Method

Three to 6 patients will be enrolled to Cohort 1a (that is, Cohort D1a or T1a; refer to [Table JSCC.1](#) and [Table JSCC.2](#) for LY3022855-plus-durvalumab and LY3022855-plus-tremelimumab combinations, respectively). If none of the first 3 patients or 1 of 6 patients in Cohort 1a experiences a DLT event, enrollment to the next “a” cohort will proceed (that is, to Cohort 2a, and so on). However, if 1 of 3 patients in any cohort (that is, at any dose level) experiences a DLT, up to 3 additional patients will be enrolled at that dose level. If a DLT is observed in ≥ 2 of a maximum of 6 patients in Cohorts 1a, 2a, 3a, or 4a, concurrent enrollment of 3 to 6 patients to each of the respective “b”, “c”, and “d” cohorts (as applicable) will occur and no higher dosages will be explored. For example, if no DLTs are noted in Cohort 1a, enrollment to Cohort 2a will occur; however, if 2 patients in Cohort 2a experience DLTs, enrollment to Cohorts 2b and 2c will occur concurrently and no higher dosages will be studied. An exception to this method is that enrollment to Dnb/Tnb cohorts will occur only if ≥ 2 DLTs are observed after Cycle 1, Day 21 of the corresponding Dna/Tna cohorts. All patients will be assigned to treatment cohorts by the sponsor, with patients assigned sequentially to the “b”, “c”, and “d” cohorts.

The MTD identified for each combination therapy in Part A will then be the dosage used (confirmed) in Part B (Phase 1b/disease-specific expansion). However, if each of the “b”, “c”, and “d” cohorts (as applicable) in Part A are observed to have a probability of causing a DLT that is lower than 33%, the sponsor (in consultation with the collaborator) will select the dosage to be used in Part B, based on clinical or correlative study results.

Table JSCC.3. MTD Determination for the Combination of LY3022855 plus Durvalumab

Cohort	Number of Patients Who Experience a DLT (in Cycle 1)		
	0 of 3	1 of 6	≥2
D1a D1b D1c	Enroll to D2a MTD is D1b MTD is D1c	Enroll to D2a MTD is D1b MTD is D1c	Enroll to D1b and D1c Not defined Not defined
D2a D2b D2c	Enroll to D3a MTD is D2b MTD is D2c	Enroll to D3a MTD is D2b MTD is D2c	Enroll to D2b and D2c MTD is D1a MTD is D1a
D3a D3b D3c	Enroll to D4a MTD is D3b MTD is D3c	Enroll to D4a MTD is D3b MTD is D3c	Enroll to D3b and D3c MTD is D2a MTD is D2a
D4a D4b D4c	MTD is D4a MTD is D4b MTD is D4c	MTD is D4a MTD is D4b MTD is D4c	Enroll to D4b and D4c MTD is D3a MTD is D3a

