8.1.2.4. Summary of AE/SAE Reporting Guidelines

The AE and SAE reporting guidelines are summarized in [Table JSCC.4](#); recommendations for reporting SAEs are presented in [Attachment 4](#).

Table JSCC.4. AE and SAE Reporting Guidelines for Study JSCC

Timing	Types of AEs/SAEs Reported	Collection Database	Lilly Safety System
Prestudy (during screening, prior to administration of study drug[s]) Starts at the signing of informed consent and ends just before the first dose of study drug.	Preexisting conditions AEs related to protocol procedures SAEs related to protocol procedures	X X X	X
On study treatment Starts the day of the first dose of study drug and ends the day the patient and investigator agree that the patient will no longer continue to receive study treatment.	All AEs All SAEs, regardless of relatedness	X X	X
30-Day Follow-Up (Visit 801) Starts the day after the patient and investigator agree that the patient will no longer continue to receive study treatment and ends when end-of-study safety assessments are completed. This visit will be extended as needed to follow any ongoing AEs at least possibly related to study drug(s) or protocol procedures.	All AEs All SAEs, regardless of relatedness	X X	X
90-Day Follow-Up (Visit 802) (only for durvalumab and tremelimumab safety) Occurs 90 days (± 7 days) after the patient and investigator agree that the patient will no longer continue to receive study treatment. This visit will be extended as needed to follow any ongoing AEs at least possibly related to study drug(s) or protocol procedures.	All AEs All SAEs, regardless of relatedness	X X	X

Timing	Types of AEs/SAEs Reported	Collection Database	Lilly Safety System
Continued Access Treatment Period (Visits 501-5XX)	All AEs All SAEs, regardless of relatedness	X X	X
Starts at the first study visit after study completion has occurred and ends when the patient and investigator agree that the patient will no longer continue to receive study treatment; applies only to patients who have not met discontinuation criteria.			
Continued Access Follow-Up (Visits 901 and 902)	All AEs All SAEs, regardless of relatedness	X X	X

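### More than 3 patients may be dosed concurrently at a Part A level, but the escalation rule gives no action for a lone DLT in patient 4 or 5 and no wait for patients still in Cycle 1

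*Protocol*

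**What the plan says.** Protocol 7.3.1 provides that, when eligible patients have consented concurrently, "more than 3 patients may be assigned to a particular dose level provided that accrual has not ceased due to excessive toxicity". The sponsor must approve after discussion with the investigators. SAP 5.2 carries the same allowance.

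The decision rule is in protocol 7.2.2.2. "If none of the first 3 patients or 1 of 6 patients in Cohort 1a experiences a DLT event", enrolment moves to the next level, and the text carries this on to later levels. The fill-up rule reads: "if 1 of 3 patients in any cohort (that is, at any dose level) experiences a DLT, up to 3 additional patients will be enrolled". If 2 or more of at most 6 patients have a DLT, enrolment to the alternative-schedule cohorts at that level "will occur and no higher dosages will be explored".

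For durvalumab, Table JSCC.3, "MTD Determination for the Combination of LY3022855 plus Durvalumab", has three outcome columns: 0 of 3, 1 of 6, and 2 or more. For tremelimumab there is no such table. Section 7.2.2.1 states "The MTD will be determined as shown in" Tables JSCC.3 and JSCC.4, but Table JSCC.4 is "AE and SAE Reporting Guidelines for Study JSCC". Only the 7.2.2.2 prose, which names both D1a and T1a, governs that combination.

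Section 7.2.2 adds a decision gate: "No dose escalation can occur without prior discussion and agreement between the investigator, the Lilly study team, and the collaborator", documented in writing. Section 10.10 plans a cohort-by-cohort safety review, and 7.6.1 defines who is evaluable.

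**The concern.** The counts in 7.2.2.2 fit a design in which patients 4 to 6 enter only after the first 3 have been read out. Sections 7.3.1 and SAP 5.2 remove that order, and two situations then have no stated action.

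- The first 3 patients are clear and patient 4 or 5 alone has a DLT. The escalation condition is met, the fill-up trigger is not, and the stop rule is not. The level stands at 1 of 4 or 1 of 5, and the prose lets the next level open.
- The first 3 are clear and concurrently dosed patients are still inside the 28-day DLT window. Nothing makes escalation wait for them. Section 10.10 does mention all evaluable patients completing the DLT period, but as the time for an optional interim analysis to plan further studies, not as a condition for escalation.

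At stake is whether DLT information from patients already exposed at a level, observed or pending, must count before others receive a higher dose.

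**Working it through.** **Inputs.** The rules are those of 7.2.2.2 and 7.3.1. The DLT window is Cycle 1, 28 days (7.2.2.1 and 7.6.1). The documents give no true DLT rate, so p is assumed at 25%, 33%, 40% and 50%; 33% is the MTD threshold in 7.2.2.1. How often more than 3 patients will be dosed is not stated, so results are conditional on 4, 5 or 6 treated. Concurrent patients are taken to count toward the 6, and a fill-up is taken to go to 6. Write q = 1 − p.

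**The plan's own figures.** The Part A sizes in 10.1 reproduce with at most 6 patients per cohort:
- minimum 4 × 3 = 12 per combination;
- durvalumab maximum 4 × 6 + 2 × 6 = 36;
- tremelimumab maximum 4 × 6 + 3 × 6 = 42;
- total 36 + 42 = 78.

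**How often the unlisted count arises, at p = 0.33** (q³ = 0.3008):
- 4 treated, first 3 clear, patient 4 has a DLT: q³p = 0.3008 × 0.33 = 0.099.
- 5 treated, first 3 clear, exactly one later DLT: q³ × 2pq = 0.3008 × 0.4422 = 0.133.

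**Probability of escalating, everyone read out, stop clause applied, p = 0.33** (q⁵ = 0.1350). The changed rule fills any single DLT in fewer than 6 patients up to 6.
- Sequential 3+3: q³ + 3pq⁵ = 0.301 + 0.134 = 0.434.
- 4 treated. As written: q³ + 3pq⁵ = 0.434. Changed: q⁴ + 4pq⁵ = 0.2015 + 0.1782 = 0.380.
- 5 treated. As written: q³(1 − p²) + 3pq⁵ = 0.268 + 0.134 = 0.402. Changed: q⁵ + 5pq⁵ = 0.358.
- 6 treated. Both: q⁶ + 6pq⁵ = 0.358.

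The gap for 4 treated can be checked another way. A level at 1 of 4, if filled, reaches 2 or more of 6 with probability 1 − q² = 0.551, and 0.099 × 0.551 = 0.055. For 5 treated, 0.133 × 0.33 = 0.044.

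| Assumed DLT rate | 4 treated: as written / changed | 5 treated: as written / changed |
|---|---|---|
| 25% | 0.600 / 0.554 | 0.573 / 0.534 |
| 33% | 0.434 / 0.380 | 0.402 / 0.358 |
| 40% | 0.309 / 0.254 | 0.275 / 0.233 |
| 50% | 0.172 / 0.125 | 0.141 / 0.109 |

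The gap is 3.1 to 5.5 percentage points before rounding.

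**Open window, p = 0.33.** Suppose the next level opens as soon as the first 3 are clear and no later patient has been read out. This is the extreme case. The share of these decisions that the changed rule would reverse is:
- 4 treated: p(1 − q²) = 0.33 × 0.551 = 18%.
- 5 treated: p² + 2pq × p = 0.109 + 0.146 = 25%.
- 6 treated: P(2 or more of 3) = 3p²q + p³ = 0.219 + 0.036 = 25%.

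**The case against.** The strongest reply is that this is a gap in wording rather than an instruction to escalate. In Table JSCC.3 the only column with a single DLT is 1 of 6, and the prose also ties escalation after a DLT to 1 of 6. Read together they suggest filling up. A reader might infer that the protocol affirmatively allows escalation on 1 of 4 or 1 of 5 in both combinations. For durvalumab that goes too far: the table leaves those counts unlisted, and only the literal prose lets them through. For tremelimumab the prose stands alone.

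The decision gates also matter. A DLT in patient 4 or 5 belongs to the dose-level data reviewed under 10.10, and escalation needs documented three-party agreement. A cautious team could fill to 6. This makes a poor decision less likely, but none of these sections gives an action for 1 of 4 or 1 of 5, or a wait.

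Three other inferences fail:
- **That the trial escalates too readily.** The rule as written never escalates more often than a sequential 3+3. The gap above is measured against a stricter rule.
- **That two or more DLTs could be passed over once seen.** The stop clause covers them.
- **That the open-window harm is the chance of any later DLT**, 1 − q^(n−3) with n treated, which at 33% is 33%, 55% and 70% with 4, 5 and 6 treated. One DLT does not by itself bar escalation even under the changed rule, since 1 of 6 escalates. The decision-relevant figures are 18%, 25% and 25%, and those are upper bounds.

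Finally, waiting does cut against the purpose of 7.3.1, which is to accommodate patients with advanced disease. That is a real cost, limited to about one cycle.

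**Conclusion.** The point holds as a minor to moderate safety matter that should be corrected. The protocol allows 4 to 6 patients at a level from the start, yet its prose decides on the first 3 and triggers fill-up only on 1 of 3. A lone later DLT, or an open Cycle 1 window, can therefore be disregarded without departing from the text.

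The effect is limited. It arises only with sponsor-approved enrolment of more than 3. With everyone read out it is about 5 points on the probability of escalating at an assumed 33% rate with 4 treated, about 4 points with 5, and zero with 6. The unconditional effect is smaller and cannot be computed, because the frequency of such cohorts is unknown.

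For durvalumab, the 33% toxicity pause in Part B (7.2.3) and possible revision of the RP2D (10.1) are later safeguards. Tremelimumab has no Part B and no RP2D objective in the current protocol, so the consequence there is which higher doses Part A patients receive.

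**What to change.** In 7.2.2.2 and Table JSCC.3, and in an equivalent tremelimumab table cited from 7.2.2.1 in place of Table JSCC.4, base each decision on all evaluable patients dosed at the level. Take it once each has completed Cycle 1 or had a DLT, or as soon as 2 DLTs occur. Cross-refer to this from SAP 5.2.

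- 0 DLTs in 3 to 6 patients: escalate.
- 1 DLT in 3, 4 or 5 patients: fill to 6, and escalate only on 1 of 6.
- 2 or more DLTs: existing rule unchanged.

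The drafting cost is a few sentences and some table columns. Escalation may wait up to about one cycle (28 days) for the last concurrent patient, and about one more cycle when a level is filled. At 33%, the added filling averages 2 × 0.099 = 0.20 patients per cohort with 4 treated and 1 × 0.133 = 0.13 with 5 treated. No cohort exceeds 6, so the planned maximum of 78 does not change.

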7.3.2. Part B: Disease-Specific Expansion (Phase 1b)

A patient who meets all criteria for enrollment will be assigned (by the sponsor) to a treatment cohort, based on the patient's diagnosis at baseline.

7.4. Blinding

This is an open-label study.

7.5. Concomitant Therapy

All concomitant medications should be recorded throughout the patient's participation in the study. The principal investigator must be informed as soon as possible about any medication taken from the time of screening until the end of the clinical phase of the study (final study visit). Appropriate documentation for all forms of premedications, supportive care, and concomitant medications, including herbal preparations, must be captured on the case report form (eCRF).

7.5.1. Excluded Concomitant Therapy

Other than the study treatment to which the patient is assigned (Section 7.2) and any required contraceptive (Section 6.1.1), no other chemotherapy, immunotherapy, cancer-related biologic or hormone therapy, herbal preparation intended to treat cancer, or experimental drugs will be permitted while the patient is on this study. Palliative radiotherapy may be allowed after consultation with the sponsor. Disease progression requiring other forms of antitumor therapy will necessitate discontinuation of the study treatment.

The following are also not permitted during the study:

- Immunosuppressive medications including, but not limited to systemic corticosteroids at doses not exceeding 10 mg/day of prednisone or equivalent, methotrexate, azathioprine, and tumor necrosis factor (TNF)- α blockers.
 - Use of immunosuppressive medications for the management of investigational product-related AEs or in patients with contrast allergies is permitted.
 - Use of inhaled and intranasal corticosteroids is permitted.
 - A temporary period of steroids will be permitted for different indications, at the discretion of the principal investigator (for example, chronic obstructive pulmonary disease, radiation, nausea, etc.).
- Live attenuated vaccines within 30 days of Cycle 1, Day 1 dosing (that is, 30 days prior to the first dose of study treatment, during study treatment, and for 30 days postdiscontinuation of study treatment).
 - Inactivated vaccines, such as the injectable influenza vaccine, are permitted.

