Abbreviations: ALT = alanine aminotransferase; ANC = absolute neutrophil count; aPTT = activated partial thromboplastin time; AST = aspartate aminotransferase; GFR = glomerular filtration rate; INR = international normalized ratio; PT = prothrombin time; PTT = partial thromboplastin time; T4 = thyroxine; TSH = thyroid-stimulating hormone; ULN = upper limit of normal.

^a GFR should be estimated via the Chronic Kidney Disease Epidemiology Collaboration (CKD-EPI) creatinine equation (Levey et al. 2009).

[8] Have a performance status of ≤ 1 on the Eastern Cooperative Oncology Group (ECOG) scale (refer to [Attachment 5](#)).

[9] Have discontinued previous treatments for cancer and recovered from the acute effects of therapy.

At the discretion of the investigator, patients with hormone-refractory prostate cancer who are stable on gonadotropin-releasing hormone (GnRH) agonist therapy or maintenance prednisone, and patients with breast cancer who are stable on antiestrogen therapy (for example, an aromatase inhibitor) may have that treatment continued while they are enrolled.

[10] Are reliable and willing to make themselves available for the duration of the study and are willing and able to comply with the protocol for the duration of the study, including undergoing treatment, scheduled visits and examinations (including follow-up), and attempted pretreatment and on-treatment tumor biopsies (Part A – all cohorts and Part B – ovarian cancer cohort only).

[11] Have an estimated life expectancy, in the judgment of the investigator, of at least 12 weeks.

[12] Male patients:

[a] who are sterile (including vasectomy)

or

[b] who are not sterile and agree to use 2 acceptable methods of effective contraception* during the study, starting at screening, for at least 6 months following last dose of study drug(s); and agree not to donate sperm during the study and for at least 6 months following last dose of study drug

[13] Female patients:

[a] are women not of childbearing potential due to surgical sterilization (at least 6 weeks postsurgical bilateral oophorectomy with or without hysterectomy or tubal ligation) confirmed by medical history, or postmenopausal by history. Postmenopausal women include women with either:

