7.5.2. Permitted Concomitant Therapy

Concurrent use of hormones for noncancer-related conditions (insulin for diabetes, hormone replacement therapy) is permitted.

Patients should receive concomitant medications or treatments deemed necessary by the investigator to provide adequate prophylactic or supportive care, including acetaminophen or diphenhydramine, antibiotics, nutritional support, growth factor support (except granulocyte colony-stimulating factor [G-CSF] or granulocyte macrophage colony-stimulating factor [GM-CSF]), or therapy for correction of metabolic disorders, optimal symptom control, and pain management. If clinically indicated at any time during the study, erythropoietin and transfusions (packed red blood cells, whole blood, platelets, or plasma) may be used according to American Society of Clinical Oncology (ASCO) guidelines (Rizzo et al. 2010).

Refer to Section 7.2.1.1 for information regarding premedication for IRRs.

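### Protocol Section 7.5.1 sets the prednisone limit the wrong way round and bans hormone therapy that Inclusion Criterion 9 lets patients keep

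*Protocol*

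**What the plan says.** Section 7.5.1 of the protocol (Excluded Concomitant Therapy) contains two rules that matter here.

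- **Hormones.** Apart from assigned study treatment and any required contraceptive, it allows "no other chemotherapy, immunotherapy, cancer-related biologic or hormone therapy" while the patient is on study.
- **Steroids.** Its list of further prohibited items gives, as an example of immunosuppressive medication, "systemic corticosteroids at doses not exceeding 10 mg/day of prednisone or equivalent". Three sub-items relax this. The first reads "Use of immunosuppressive medications for the management of investigational product-related AEs or in patients with contrast allergies is permitted". The second, on local routes of administration, reads "Use of inhaled and intranasal corticosteroids is permitted". The third, on short courses, reads "A temporary period of steroids will be permitted for different indications, at the discretion of the principal investigator".

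Section 7.5.2 adds: "Concurrent use of hormones for noncancer-related conditions (insulin for diabetes, hormone replacement therapy) is permitted".

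Inclusion Criterion 9 (Section 6.1.1) gives a permission that lasts through enrolment. At the investigator's discretion, two groups may continue their existing treatment. The first group is "patients with hormone-refractory prostate cancer who are stable on gonadotropin-releasing hormone (GnRH) agonist therapy or maintenance prednisone". The second group is "patients with breast cancer who are stable on antiestrogen therapy". The criterion states no prednisone dose.

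Exclusion Criterion 18 (Section 6.1.2) exempts physiological systemic steroid doses up to 10 mg/day of prednisone. Exclusion Criterion 21 accepts treated CNS metastases provided, among other conditions, that the steroid dose is not above 10 mg/day.

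**The concern.** A prohibited list would be expected to name doses above the threshold that the eligibility criteria use. This one names doses at or below it. Separately, the hormone ban makes no reference to the patients whom Criterion 9 admits on the understanding that their endocrine therapy may go on.

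What is at stake is trial conduct. A site that reads 7.5.1 as binding has to withdraw stable therapy from a patient whom Criterion 9 allows to keep it, or log its continuation as a deviation. A site that reads Criterion 9 as governing does neither. The same patient could therefore be handled and recorded differently at different sites.

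**Working it through.** No sample size, error rate or estimate depends on this point, so the check is a comparison of texts and a count.

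**1. Which way the 10 mg/day limit runs**

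| Place in protocol | Applies | 10 mg/day or less | Above 10 mg/day |
|---|---|---|---|
| Criterion 18 | Screening | Exempt from the exclusion | Excluded |
| Criterion 21 (treated CNS metastases) | Screening | Tolerated by implication | Not eligible |
| Criterion 9 (maintenance prednisone) | On study | May continue; no dose stated | Already shut out at entry by Criterion 18 |
| Attachment 7 (endocrinopathy needing continued steroid replacement) | On study | A condition for resuming study drug | Condition not met |
| Section 7.5.1 | On study | Named as prohibited | Also prohibited, because the list is open-ended |

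Section 7.5.1 is the only row that treats the low range as unacceptable. Criteria 18 and 21 are screening rules, so they conflict with it only by implication: a patient admitted on such a dose then meets a ban on that dose. Criterion 9 conflicts with it directly, because its permission applies on study.

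**2. Whether the exceptions rescue low-dose prednisone**

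The sub-items in 7.5.1 contain four exceptions: product-related adverse events, contrast allergy, inhaled or intranasal use, and a temporary course. Continuous maintenance prednisone for prostate cancer fits none of them: 0 of 4.

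**3. Whether anything rescues the hormone therapies**

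The hormone sentence has two exceptions, study treatment and required contraceptives. A GnRH agonist for prostate cancer and an antiestrogen for breast cancer are neither. Section 7.5.2 permits hormones for noncancer-related conditions only, which leaves both out. Neither section refers to Criterion 9.

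**4. Count**

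Treatments that Criterion 9 lets continue and 7.5.1 bars: 2 hormonal (GnRH agonist, antiestrogen) + 1 corticosteroid (maintenance prednisone at 10 mg/day or less) = 3, which is every treatment Criterion 9 names.

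**5. Reach**

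- Part B, as planned, enrols only NSCLC and ovarian cancer (Criterion 2), so the hormone conflict falls in Part A. Section 7.2.3 allows cohorts of other histologies to be added, which could extend it.
- The steroid item applies in both parts.
- SAP Section 6.15 summarises major violations only. Neither document says whether a deviation of this kind would be graded major, so it might not appear in the report.

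**The case against.** The strongest reply is that this is a drafting slip with little consequence. It has four parts.

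- **The error is in the safe direction.** Because the list is not exhaustive, doses above 10 mg/day stay barred outside the exceptions. The text over-restricts low doses and does not open the way to high ones. This stands.
- **Other text covers much low-dose use.** Section 7.5.2 allows noncancer hormone replacement and necessary supportive care, which can reasonably include physiological steroid replacement. Steroids for an endocrinopathy caused by study drug fall under the product-related adverse event exception, so Attachment 7 shows only which way the threshold should run and is not a second conflict. This stands and narrows the gap. What remains is chiefly maintenance prednisone under Criterion 9 and other chronic low-dose use that is not replacement.
- **A specific permission would override a general ban.** Sites may well read it that way, and the discontinuation rule in Section 6.3.2 is triggered by beginning alternative anticancer therapy, which does not describe therapy carried over from before entry. So no text requires such a patient to be withdrawn. But the protocol states no order of precedence, Criterion 9 is discretionary and 7.5.1 is mandatory. A site cannot be sure which governs.
- **No measurable impact is shown.** This is correct as to size, and it limits the weight of the point. It does not make the rule right: 7.5.1 is a current treatment instruction and contradicts another current instruction.

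**Conclusion.** The concern holds. Section 7.5.1 is wrong as written in two places: the steroid threshold is reversed, and the hormone ban lacks an exception for Criterion 9. Between them they prohibit all three treatments that Criterion 9 allows.

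The consequence is limited to which ongoing therapy patients may keep and how deviations are recorded. The number affected cannot be given, since neither document counts patients on these drugs.

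The conclusion rests on two readings: that Criterion 9 is an on-study permission, as its wording indicates, and that 10 mg/day is meant as a ceiling, as Criteria 18 and 21 and Attachment 7 indicate. The protocol should be corrected, but nothing in the statistical analysis depends on it.

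**What to change.** Amend Section 7.5.1 in two places.

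1. In the corticosteroid item, delete the word *not* from the dose phrase, so that the prohibition applies to doses exceeding 10 mg/day.
2. In the sentence on hormone therapy, add an exception for therapy continued under Inclusion Criterion 9, with any maintenance prednisone at no more than 10 mg/day.

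No further exception is needed in the corticosteroid item. After the first edit, prednisone up to 10 mg/day is allowed there, and Criterion 18 excludes higher doses at entry. The prednisone clause in the second edit is not redundant: a site could read prednisone given for prostate cancer as cancer-related hormone therapy, and the cap keeps the exception in line with Criterion 18 without widening eligibility.

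The cost is two phrases in a protocol amendment, with no change to design, sample size or analysis.
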